# 9 STATISTICAL CONSIDERATIONS

#### 9.1 Sample size

The sample size for this trial will be adaptively determined through a phase 2/3 design. Enrollment is planned to last approximately 2 months. Each patient will be randomly allocated to Reparixin or Control according to a randomization ratio of 2:1 and he/she will be followed for the entire treatment and follow-up duration for collecting the efficacy endpoints of each study phase.

For the Phase 2 portion of the study, the primary analysis will compare Reparixin versus Control in terms of time to a composite endpoint (primary endpoint of phase 2) including the following events: requirement of supplemental oxygen treatment, mechanical ventilation use, admission to ICU, and any requirement of rescue medication. Based on clinical experience, an improvement of the median time freedom from composite event of 1.5 times is expected. Assuming an exponential distribution, a total sample size of 48 patients will allow to provide 80% power to show superiority of Reparixin compared to control using a log-rank test at a one-sided significance level of 0.025.

The sample size for the phase 3 is based on assessment of superiority of Reparixin compared to control arm in terms of freedom from a composite endpoint (primary endpoint of phase 3) of severe events including death, admission to the ICU, requirement of mechanical ventilation.

Based on same assumptions of phase 2 regarding randomization (2:1) and expecting to double the median time freedom from severe composite event using Reparixin compared to control (from 2-4 to 4-8 days), a total sample size of 111 patients will allow to achieve a power of 90% to show superiority of Reparixin over control using a log-rank test at a one-sided significance level of 0.025. No drop-out are expected to happen. The number of patients to be included may be revised based on considerations from Phase 2 data analysis.

Primary endpoint of phase 3 will be tested only if superiority of Reparixin is shown in phase 2. Thus, the overall type I error of the study will be controlled at 0.025 via the hierarchical testing procedure.

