Interim #1	~60	p-value <0.00296	p-value ≥0.26674
Interim #2	~81	p-value <0.00892	p-value ≥0.09841
Final	111	p-value <0.02151	p-value ≥0.02151

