3.2 Sample size justification

The sample size of the full phase 2/3 study is calculated based on data from clinical experience and on Sponsor expectations as reported in Table 2:

Table 2: Assumptions for primary endpoints

Primary endpoint*	Standard of care (control)	Reparixin
Time to primary endpoint of phase 2	2 days	5 days
Time to primary endpoint of phase 3	2-4 days	4-8 days

* see section 3.5.1.

Based on the following assumptions:

- an enrollment phase of 2 months,

- a total follow-up of 21 days,
- a randomization ratio (reparixin:control) of 2:1
- an exponential distribution for survival probability $S(t) = e^{-\lambda t}$,
- a comparison between treatment by means of a log-rank test,
- an interim analysis framework as described in section 4.5, and
- a correction of the type I and II errors by means of O'Brien-Fleming spending functions

a total of 109 events (corresponding to approximately 111 subjects) will allow to provide >80% power to show superiority of reparixin vs standard of care in terms of primary endpoint of phase 3, controlling the type I error under 0.025.

Based on the same assumptions reported above, phase 2 portion of the study will be performed when a total of 46 events (corresponding to approximately 48 subjects) has happened. This allow to achieve approximately 80% power to show superiority of reparixin vs standard of care in terms of (not severe) primary endpoint of phase 2, controlling the type I error under 0.025.

The remaining portion of the 111 patients will be enrolled in the phase 3 study segment. Anyhow, due to the novel nature of the COVID-19 pandemic and being the primary efficacy endpoint planned in phase 3 not well established, it may require confirmation based on phase 2 data. For this reason, at the end of the phase 2 portion, power calculations may be reassessed, and sample size may be re-estimated for phase 3.

The adaptive design allows for the assessment of efficacy endpoint in phase 2 which are then seamlessly confirmed in the phase 3. Since primary endpoint of phase 3 will be tested only if superiority of reparixin is shown in phase 2 (at interim or final stage), the overall type I error of the study will be controlled at 0.025 via the hierarchical testing procedure.

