3.4 Overview of planned statistical analyses

The study plans for the following statistical analyses:

- Phase 2:
 - Interim analysis for efficacy or futility: this analysis will be conducted by Data Monitoring Committee (DMC) when half of the planned events of primary endpoint of phase 2 has happened;

- Final analysis: this analysis will be conducted when all randomized phase 2 subjects has performed the final visit.
- Phase 3 (in case of success of phase 2):
 - Interim analyses for efficacy or futility: this analysis will be conducted by DMC when approximately 55% and 74% of the planned severe events of primary endpoint of phase 3 has happened;
 - Final analysis: this analysis will be conducted all randomized phase 3 subjects has performed the final visit.
- Analyses for the DMC: these analyses will be produced periodically according to the DMC charter. In addition to the above interim analyses, analyses for safety integrity reviews will be performed according to DMC charter.

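### The phase 3 interim looks are tabulated at about 60 and 81 patients, but the SAP's event trigger needs about 69–80 and 91–104 enrolled, and the protocol states no trigger

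*Protocol*

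**What the plan says.** Protocol section 9.4.5, Table 2, has one timing column, sample size, with entries of about 60, about 81 and 111. Its first row reads "Interim #1 ~60 p-value <0.00296". The protocol gives no event count for either interim look. Section 9.2 describes only when the final phase III analysis takes place.

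The SAP sets the timing by events. Section 3.4 places the looks when "approximately 55% and 74% of the planned severe events of primary endpoint of phase 3 has happened", and section 3.2 plans "a total of 109 events (corresponding to approximately 111 subjects". Since 60/109 = 55% and 81/109 = 74%, the triggers are 60 and 81 events. SAP section 4.5, Table 5, nevertheless pairs about 60 patients with 60 events and about 81 patients with 81 events. The phase 2 table beside it keeps the two quantities apart: about 27 patients for 23 events.

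**The concern.** Sixty events among about 60 patients would require every enrolled patient to have died, been admitted to the ICU or been ventilated by the time of the look. That cannot be expected while recruitment continues, and the plan itself foresees two event-free patients among 111 after full follow-up. The two documents can therefore start the looks at different times. Looks with less information than the bounds assume make the efficacy bounds too lenient and the futility bounds too strict. If the event trigger is followed instead, the data monitoring committee and the sponsor plan around patient numbers that are too low.

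**Working it through.** **Inputs.**
- Test: "using a log-rank test at a one-sided significance level of 0.025" (protocol 9.1).
- Power: "a total sample size of 111 patients will allow to achieve a power of 90" per cent (protocol 9.1); the SAP says "a total of 109 events (corresponding to approximately 111 subjects) will allow to provide >80% power" (3.2).
- Effect: "expecting to double the median time freedom from severe composite event using Reparixin compared to control (from 2-4 to 4-8 days" (protocol 9.1). With exponential times the hazard ratio is 2/4 = 4/8 = 0.5.
- Allocation: "a randomization ratio (reparixin:control) of 2:1" (SAP 3.2).
- Follow-up 21 days and enrolment 2 months (SAP 3.2), taken as 2 × 30.4375 = 60.9 days (SAP Table 7 conversion). No drop-out (protocol 9.1).
- My assumption: 111 patients enrolled uniformly over the 60.9 days.

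**1. Reproduce the planned events.** Expected events = 111 × [1/3 (1 − 2^(−21/2)) + 2/3 (1 − 2^(−21/4))] = 111 × 0.982 = 109.0. This is the SAP's figure, so it rests on medians 2/4. Medians 3/6 give 104.2 and 4/8 give 98.0.

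**2. Reproduce the bounds.** Classical O'Brien-Fleming bounds are z = C/√t, with C solved for one-sided 0.025.
- t = 60/111, 81/111, 1: C = 2.024, p = 0.00296 / 0.00892 / 0.02151, exactly as printed.
- t = 60/109, 81/109, 1: p = 0.00316 / 0.00937 / 0.02137, not as printed.

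The printed futility bounds solve back to 108.8 events, looks at 58.8 and 79.4 events, and 90.0% power. The stated design reproduces.

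**3. Patients enrolled when the events occur.** When the nth patient is enrolled, expected events are the sum over patients of 1/3·F_control(x) + 2/3·F_reparixin(x), where x is time since that patient's entry, capped at 21 days. Check on phase 2 (48 patients over 60.9 days, medians 2/5 from SAP Table 2): 23 events occur at 27.8 enrolled, against about 27 in the table. For phase 3:

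| Medians (days) | Enrolled at 60 / 81 events | Events at 60th / 81st enrolment | Final events from 111 |
|---|---|---|---|
| 2/4 | 69 / 91 | 51 / 72 | 109 |
| 3/6 | 75 / 97 | 46 / 66 | 104 |
| 4/8 | 80 / 104 | 42 / 61 | 98 |

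Accrual matters. If the 48 phase 2 patients count towards the 111 and are already fully followed, with 63 more over two months, medians 2/4 give about 66 and 87.

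**4. Operating characteristics of the printed bounds.** Information = events × 2/9, log hazard ratio = ln 2, so the drift at 109 events is 0.693 × √(109 × 2/9) = 3.41. Boundary-crossing probabilities are by recursive integration. Type I error ignores futility, which the protocol calls non-binding; power obeys it.

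| Reading of the looks | Events at looks and end | Type I error | Power | Interim futility stops at HR 0.5 |
|---|---|---|---|---|
| SAP event trigger | 60 / 81 / 109 | 2.49% | 90.3% | 6% |
| 60 and 81 patients with 21 days completed, 2/4 | 58.9 / 79.6 / 109 | 2.50% | 90.1% | 6% |
| 60th and 81st enrolment, 2/4 | 51 / 72 / 109 | 2.59% | 88.3% | 8% |
| 60 and 81 patients with 21 days completed, 4/8 | 53 / 71.5 / 98 | 2.50% | 86.8% | 8% |
| 60th and 81st enrolment, 4/8 | 42 / 61 / 98 | 2.63% | 83.4% | 12% |

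In the third row the two conventions matter: with futility ignored, power is 92.2%; with it obeyed, type I error is 2.18%.

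**The case against.** The best defence is that the column means patients with completed follow-up. The efficacy bounds fit 60/111 and 81/111 exactly, and 60 × 0.982 = 58.9 and 81 × 0.982 = 79.6 are almost the look sizes implied by the futility bounds. On that reading SAP Table 5 is off by about one event per row, and with medians 2/4 the design keeps 2.50% and 90.1%. In addition, SAP 3.4 already states an event trigger, and SAP 4.7 requires a protocol amendment and an updated SAP before phase 3.

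Much of this stands. A reader might infer that event counts were simply printed in the patient column; the bounds do not bear that out, and the origin of the numbers cannot be settled from the documents. A reader might also infer that the plan inflates type I error to 2.6–2.7% and cuts power to 84–89%. That needs looks at the moment of the 60th and 81st enrolment, which neither document states. The two harms also come from opposite handling of futility, so they do not occur together.

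The defence does not rescue the tables. Completed follow-up is stated nowhere and is not the SAP's trigger. It would not make 60 and 81 the enrolment either: at 111/60.9 = 1.82 patients a day, another 38 enter in 21 days, giving about 98 at the first look and all 111 at the second.

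**Conclusion.** The point holds as an inconsistency in a figure that sets interim timing. The protocol gives patient numbers without a trigger. The SAP gives an event trigger beside patient numbers that do not fit it, about 9–20 too low at the first look (69 to 80 against 60) and 10–23 too low at the second (91 to 104 against 81). These ranges rest on uniform two-month accrual of 111 patients and the SAP's range of medians.

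The documents do not support a claim that the design fails. Under the SAP's event trigger the printed bounds hold type I error at 2.49% and power at 90.3%. The shift to about 2.6% and 88% (medians 2/4) is conditional on the enrolment reading. It grows with longer medians, but part of that further power loss comes from having only 98 final events with medians 4/8: power is already 86.8% there when the looks wait for completed follow-up.

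**What to change.** 1. In protocol Table 2 and SAP Table 5, state the trigger as 60 and 81 of 109 primary events, in line with SAP 3.4.
2. Replace about 60 and about 81 by expected enrolment at those counts: about 69 and 91 with medians 2/4, up to 80 and 104 with 4/8. Label these approximate and dependent on accrual.
3. Recompute the O'Brien-Fleming bounds at the event fractions used. At 60/109 and 81/109 the efficacy bounds are 0.00316 / 0.00937 / 0.02137; with the printed interim futility bounds these give 2.50% type I error and 90.3% power at 109 events. Re-derive the futility bounds on the same fractions, and provide for recalculation from the events actually observed at each look.

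The cost is an edit to two tables and one short calculation, which can go into the amendment that phase 3 already requires. The drawback is that an early stop spares fewer patients than the tables imply: 111 − 69 = 42 and 111 − 91 = 20 with medians 2/4, or 31 and 7 with 4/8, instead of 51 and 30.

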#### **10 SUPPORTING DOCUMENTATION**

#### 10.1 Clinical and non clinical pharmacology

Reparixin (DF1681Y) is a specific inhibitor of CXC ligand 8 [CXCL8; formerly interleukin (IL)-8] biological activity, stemming from a program of drug design of molecules intended to modulate chemokine action. Reparixin is the first low molecular weight blocker of CXCL8 biological activity in clinical development. Relevant pre-clinical, toxicological and phase 1 to 3 clinical data are summarized below. It is anticipated that data on human exposition to oral 1200 mg TID, as proposed in this trial, is available from the study REP0111 (Phase 1b pilot study to evaluate reparixin in combination with chemotherapy with weekly paclitaxel in patients with HER-2 negative metastatic breast cancer). In particular from the pharmacokinetics data at the 21st day of treatment with 1200 mg reparixin oral tablets (i.e. no paclitaxel from day 15th) sufficient elements are available to estimate the drug concentration (mean) at the steady state. The Css at steady state (after repeated oral administration) can calculated form the following formula: Css = AUC/ $\tau$  where AUC is the area under curve (mg\*h/ml) and  $\tau$  is the dose interval (h). The mean AUC 0-8h( $\tau$ ) at 21st day is 191 mcg\*h/ml, the interval of dose is 8 hours; consequently the mean Css is 23,88 mcg/ml, which is comparable to the Css obtained by IV continuous infusion. Please also refer to the Investigator's Brochure for more detailed information.

Reparixin (formerly repertaxin) was granted orphan drug designation for the "prevention of delayed graft function after (solid) organ transplantations" by the European Commission of Orphan Medicinal Products in September 2001 and by the Food and Drug Administration in January 2003. Recently orphan drug designation has been grated in the EU for "prevention of graft rejection in pancreatic islet transplantation". In the 4th quarter of 2011, Dompé has received Scientific Advice from the European Medicines Agency (EMA) for the development of reparixin in pancreatic islet transplantation.

#### **10.1.1 RELEVANT NON-CLINICAL PHARMACOLOGY**

Reparixin is *in vitro* a potent and specific inhibitor of CXCL8 biological activity. *In vitro* chemotaxis experiments have shown that reparixin inhibits CXCL8-induced chemotaxis of human polymorphonuclear leukocytes (PMN) in the low nanomolar range. Studies to elucidate the mechanism of action have shown that reparixin is a non-competitive allosteric inhibitor of the CXCL8 receptors CXCR1 and CXCR2. Interaction of reparixin with CXCL8 receptors inhibits the intracellular signal transduction events activated by binding of CXCL8 to CXCR1 and CXCR2 [Bertini, 2004; Allegretti, 2005]. In vivo, reparixin prevented PMN infiltration into the transplanted kidney and reduced creatinin levels in a rat model of kidney transplantation. Similarly, in a rat model of lung transplantation, reparisin improved isolated graft oxygenation, decreased pulmonary oedema, and significantly reduced neutrophil infiltration into transplanted lungs. Moreover, reparixin prevented PMN infiltration and tissue damage in other animal models of ischemia/reperfusion injury of liver, brain, intestine, heart and spinal cord. In these models, in vivo inhibition of PMN recruitment ranged from 40 to 90%, and inhibition of tissue damage ranged from 50 to 80%. Efficacy was seen in all models at reparixin dose of 9.90 mg/kg [Bertini, 2004; Cugini, 2005; Souza, 2004; Cavalieri, 2005; Garau, 2005; Villa, 2007; Gorio, 2007]. More recently, reparixin lysine salt was evaluated in different models of intrahepatic pancreatic islet transplantation in mice, which include syngeneic and allogeneic settings. Reparixin was administered by s.c. continuous infusion for 7 or 14 days starting from day -1 of islet transplantation. A dose of 5.28 mg/kg/hour was administered in all experiments. Reparixin was able to significantly improve islet engraftment, as demonstrated by its ability to increase the likelihood of and to reduce the time to gain non-fasting blood glucose levels less than 200 mg/dl (normo-glycaemia) in marginal mass syngeneic islet transplantation model. In the fully mismatched allogeneic model, reparixin not only protected islets

from early graft failure, but was also able to increase the time to rejection, as shown by post-transplant prolongation of normo-glycaemia. Graft function was indefinitely prolonged in 20/30% of mice treated with reparixin and rapamycin, suggesting possible tolerance induction. In parallel, reparixin treatment reduced intrahepatic infiltration of PMNs, macrophages, T helper and dendritic cells.

## **10.1.2 TOXICOLOGY DATA**

Reparixin was tested for toxicity in rodent and non-rodent animal species after single and repeated i.v. doses. The repeated dose administration studies were conducted by i.v. continuous infusion, according to the intended human administration route. The general toxicological profile of i.v. reparixin, in the studies conducted to date, is characterized by a low toxicity after single or repeated dose administrations in rats (LD50 = 229.68 mg/kg i.v.; 660.00 mg/kg/day as No Observed Adverse Effect Level from 4 week studies) and mice (401.94 mg/kg i.v.). Continuous i.v. administration to dogs for 2 weeks resulted in a safe dose of 39.60 mg/kg/day. Continuous i.v. infusion of reparixin to the male and female rat at dose levels of up to 660.00 mg/kg/day did not have any significant adverse effects on mating performance and fertility. Reparixin poses no genotoxic hazard for humans.

Reparixin lysine salt, at doses in excess of those intended to be used in humans, has a safe pharmacology profile in the renal, cardiovascular and respiratory systems of rats and dogs. The local tolerability of reparixin lysine salt was assayed in the rabbit ear lateral vein. The compound was well tolerated in concentrations up to 4.95 mg/mL (1 mL/kg) infused over a minute. In order to provide evidence of the safety of DF2243Y, the main metabolite of reparixin excreted in urine in humans, safety pharmacology and toxicity studies have been performed at doses 2 to 3 times higher that those reached in man, as may occur during the treatment of patients receiving kidney transplantation.

## **10.1.3 PHARMACOKINETICS AND PRODUCT METABOLISM**

PK studies by i.v. injection revealed that reparixin is very rapidly eliminated in rats and humans (t1/2)0.5-3hrs and 1.0-1.5hrs, respectively) whereas elimination is slower in dogs (12-28hrs). The PK of reparixin was linear in rats and in dogs but linearity was less evident in humans. Reparixin undergoes complete metabolism (oxidation + conjugation) in all the species tested. The *in vitro* human hepatic, phase I metabolism of reparixin is catalysed by CYP2C9 and to a lesser extent by CYP2C19. DF2243Y, DF2188Y, methanesulfonamide and ibuprofen are the metabolites detected in human plasma and urine, with DF2243Y being the major metabolite. Exposure to ibuprofen after administration of reparixin 2.77 mg/kg/h for 48hrs (the highest dose tested in humans) was similar or lower than that obtained after a standard therapeutic single dose of ibuprofen (300mg). Preliminary PK data obtained in a few patients undergoing islet transplantation shows that plasma levels of reparixin (total and unbound) and its major metabolite DF2243Y appears to be within the expected range according to the dose administered. Due to extensive metabolism, unchanged reparixin was poorly or not excreted into the urine of rat, dogs and humans so that the PK profile of reparixin is not influenced by renal impairment. In vitro protein binding of [14C]-reparixin showed that reparixin is highly bound (approximately 99%) to plasma proteins in rats, dogs, rabbits, cynomolgus monkeys and humans. Albumin is likely to be the major binding protein in plasma in all species, accounting for 99.2% in humans.

In clinical trials with oral tablets reparixin was administered for 21 consecutive days followed by 7 days of drug holyday before the next cycle. Reparixin was rapidly absorbed (median  $T_{max}$  1 hr). Reparixin systemic exposure ( $C_{max}$  and AUClast) did not change from day 1 to day 21, indicating the absence of accumulation over the dosing period. Also  $t_{1/2}$  did not change from day 1 to day 21, with a median value of about 2 hrs. Once absorbed, reparixin is highly protein bound as only <0.1% to 0.2% of total reparixin is available as unbound (free) drug. Reparixin was rapidly metabolized to DF2243Y, DF2188Y and ibuprofen. For all three metabolites systemic exposure was similar on both day 1 and day 21 within the

observed intersubject variability. The  $t_{1/2}$  of all three metabolites appeared to remain about the same from day 1 to day 21.

To investigate the PK/PD characteristics of reparixin, we assessed the effect of the drug in inhibiting IL-8-mediated hPMN NETs release in whole blood of healthy volunteers, 500 µL/sample of whole blood were pre-incubated with vehicle or different concentrations of reparixin for 15 min at 37°C and next placed onto 13-mm polylysine coated glass circular coverslips and incubated for 30 min at 37°C in a 5% CO2 atmosphere to allow for cell adherence. Post-incubation, samples were stimulated with vehicle or IL-8 (100 ng/mL) for 4h (37°C, 5% CO2), after which the supernatant was removed and coverslips washed one time with HBSS. Next, samples were stained with 40 nM Sytox Green for 10 min. Finally, cells were fixed in 2% paraformaldehyde and NETs formation determined by confocal microscopy.

Reparixin blocked IL-8-induced NETs formation in a concentration dependent manner being the inhibition statistically significant at 5  $\mu$ g/mL (40% of inhibition) and reaching the almost complete inhibition (about 90%) at 25  $\mu$ g/mL thus confirming that the total blood concentration of 25  $\mu$ g/mL (corresponding to a free unbound concentration of 100 nM) that is reached at the steady state by iv infusion or by repeated oral administration (Css) is coherent with the objective to reach the drug exposure necessary to maximize the potential clinical efficacy of the compound.

Reparixin has some potential *in vitro* for a non-competitive inhibition of the human hepatic enzyme CYP3A4 that is involved in the metabolism of cyclosporine A, tacrolimus and rapamycin. However, since inhibition is evident at concentration far higher than the free plasma concentration of reparixin at steady state in humans, it is predicted that the clinical relevance of such inhibition is remote. Indeed, reparixin does not affect to a clinically relevant extent the activity of CYP3A4 and CYP2C9 (enzyme involved in reparixin metabolism), as revealed by an interaction study where the PK of midazolam and tolbutamide (probe substrates for these enzymes) was evaluated in healthy subjects receiving single oral doses of the probes alone or in combination with reparixin.

